### **6 Statistical Plan**

#### **6.1 Sample Size and Power Determination**

No studies have previously examined liposomal bupivacaine for pain following craniotomy. Evidence from the effectiveness of bupivacaine in a non-liposomal formulation for scalp block was analyzed for the primary endpoint of pain scores to determine an expected effect size. Descriptive statistics from the first 6 hours following surgery were used as following this point non-liposomal bupivacaine will begin to diminish in effectiveness. Based upon the effect size shown by Bala et al. ( $d=1.01$ ) in a comparison of non-liposomal bupivacaine scalp block versus placebo at 4-6 hours after craniotomy, a sample size of 30 has been determined to be necessary to achieve statistical significance ( $\alpha<.05$ ) with a power of .8. This includes an allowance for a dropout rate due to surgical revision or other factors of 10%.

## **6.2 Statistical Methods**

The primary and secondary outcome variables will be examined for group-wise differences with Analysis of Variance statistics. Significant differences in the means will then be subjected to Bonferroni's t-test. Pearson correlation coefficients will be computed for associations between variables. A p-value of <0.05 will be regarded as statistically significant.

### **6.2.1 Baseline Data**

Baseline and demographic characteristics will be summarized by standard descriptive statistics (including mean and standard deviation for continuous variables such as age and standard percentages for categorical variables such as gender).

### **6.2.2 Analysis of Primary Outcome of Interest**

The Mann-Whitney U test will be used to compare differences in subjective pain scores calculated for patients within 72 hours of surgery. All other outcomes of interest (narcotic usage, ICU length of stay, total length of stay) will be analyzed using a paired t-test.

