## Study Summary

|                           |   |
|---------------------------|---|
| Title              | Randomized study of cranial blocks for postoperative anesthesia to reduce pain and postoperative opioid usage  |
| Short Title        | Cranial blocks for postoperative anesthesia   |
| IRB Number         | 834603  |
| Protocol Number    | N/A   |
| Methodology        | Prospective single-blinded randomized controlled trial  |
| Study Duration     | 12 months   |
| Study Center(s)    | Single-center   |
| Objectives         | Primary: 

• To assess the effectiveness of analgesia by scalp nerve block with various agents in the first 72 hours following elective craniotomy.

 |
| Number of Subjects | 90  |

|  |   |
|--|---|
| Main Inclusion and Exclusion Criteria | 
Inclusion Criteria
 
 
• <math>\geq 18</math> years of age
 
• Need for elective supratentorial craniotomy
 
• Preoperative GCS <math>> 13</math>
 
 
Exclusion Criteria
 
 
• Preoperative GCS <math>\leq 13</math>
 
• Child (<math>< 18</math> years of age)
 
• Inability to understand or use the visual analog scale (VAS)
 
• Proven or suspected allergy to local anesthetics
 
• Craniotomy incision extending beyond the field of the block
 
• Patients chronically (more than 2 wk) treated with narcotic medications
 
• Previous scalp incision
 
• Bilateral craniotomies
 
• Allergies to local anesthetics
 
• GCS verbal score <math>< 4</math> after extubation
 
• Patients whose surgeries exceed 6 hrs (will be removed from study and maintained with standard of care)
 
• Patients currently on ergot-type oxytotoxic drugs, MAOIs, or certain antidepressants
 
• Lactating mother
 
 |
| Intervention                          | 
This study compares the standard of care to the standard of care plus the administration of bupivacaine or liposomal bupivacaine in patients receiving craniotomies.
   |
| Statistical Methodology               | 
A Mann-Whitney U test will be used to analyze the primary endpoint of subjects' subjective pain scores. A paired t-test will be used for all secondary endpoints.
  |

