## **3 Investigational Plan**

### **3.1 General Design**

We will employ a randomized, single-blinded, prospective study design. Patients will be randomized into one of three treatment groups: Bupivacaine, Liposomal Bupivacaine, and Saline.

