#### **5.6 Safety Evaluation**

A local safety officer will have access to unblinded data, including patient identification and drug group. [name], MD, PhD, has extensive experience with randomized controlled studies, and has served in the capacity of Safety Officer for studies. [name], in collaboration with the study coordinator, will review patient data once five subjects have been enrolled. When 15 additional subjects have been enrolled for a total of 20, [name] will again review the data. Reviews will continue at increments of 20 subjects, at enrollment totals of 40 and 60. Specifically, the Safety Officer will independently examine the primary outcome measure (i.e. cumulative pain intensity scores) and secondary outcome measures (i.e. GCS, narcotic utilization, time to rescue medication, ICU length of stay, hospital length of stay), as well as remain vigilant for any adverse events. If any adverse events are suspected, enrollment will immediately cease, the IRB will be notified, and a meeting between the Safety Officer, PI and study coordinator will take place.

[name] contact information will be provided on the study instruction sheet provided to nurses and available in the patient's chart. If any clinical staff suspects an adverse event, the study sheet provides instructions to contact the IRB and [name] immediately. Additional contact information for the PI, and the study coordinator will be listed for any concerns.

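### The primary pain analysis is specified two incompatible ways, and the Mann-Whitney version names no pair of arms and no adjustment, so the 5% level is not secured

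*Combined protocol and SAP*

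**What the plan says.** The design has three arms: "Patients will be randomized into one of three treatment groups: Bupivacaine, Liposomal Bupivacaine, and Saline". The primary analysis is described in three places.

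- Section 6.2, Statistical Methods, sets a rule for every outcome: "The primary and secondary outcome variables will be examined for group-wise differences with Analysis of Variance statistics". The follow-up to a significant ANOVA is given separately, as a multiplicity-adjusted comparison: "Significant differences in the means will then be subjected to Bonferroni's t-test". The only threshold is here: "A p-value of <0.05 will be regarded as statistically significant".
- Section 6.2.2 (Analysis of Primary Outcome of Interest) names a different test for the pain score: "The Mann-Whitney U test will be used to compare differences in subjective pain scores calculated for patients within 72 hours of surgery".
- Study Summary, Statistical Methodology, agrees with section 6.2.2: "A Mann-Whitney U test will be used to analyze the primary endpoint".

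Two further places bear on which contrast is meant. Section 6.1 takes its effect size (d = 1.01) from an external study, "in a comparison of non-liposomal bupivacaine scalp block versus placebo at 4-6 hours after craniotomy". Section 1.1 gives the trial's focus as liposomal bupivacaine against traditional local anesthetic. Section 3.4.1 defines the primary endpoint as VAS ratings repeated up to 72 hours and fixes no single per-patient summary. Section 5.6 describes the primary outcome as cumulative pain intensity.

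**The concern.** The same outcome is given two different tests, and no text ranks one above the other. All three places are current text.

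The Mann-Whitney version cannot be carried out as written. It is a two-sample test, three pairs are possible, and none is chosen. The documents point to different pairs: section 6.1 uses bupivacaine against placebo, and section 1.1 stresses liposomal against standard bupivacaine. The Bonferroni step belongs to t-tests that follow a significant ANOVA, so it does not carry over to the Mann-Whitney tests.

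Whether the primary result is declared positive can therefore turn on which section the analyst follows and how many pairs are tested. If both are settled after unblinding, the reported p-value has no defined error rate.

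**Working it through.** **Inputs from the documents.** Three arms allocated 1:1:1 (sections 3.1, 3.2); 90 patients (4.1, 4.2), so 90/3 = 30 per arm; 10% dropout, d = 1.01 and power 0.8 (6.1); p < 0.05 (6.2).

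**Assumptions.** Two-sided tests; the sample size of 30 in 6.1 is per arm; one pain score per patient. Analysed number: 30 × 0.9 = 27 per arm. Results for 24 and 30 are also given, because section 4.4 removes some patients after surgery.

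**The plan's own figure.** For one pair, n per arm = 2(1.960 + 0.842)²/1.01² = 15.4, so 16; then 16/0.9 = 17.8, so 18. The t-distribution gives 17, or 19 with dropout. The stated 30 is not reproduced this way. That is a separate reporting matter and leaves room for an adjustment.

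**Error by formula, no arm differing.**

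- One prespecified pair: 5%.
- Two pairs: 1 − 0.95² = 9.75% if independent. Allowing for the shared arm, 9.1%.
- Three pairs: 1 − 0.95³ = 14.3% if independent. The exact large-sample value is the chance that the studentized range of three groups exceeds 1.960 × √2 = 2.772, which is 12.2%.

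**Error by simulation.** 40,000 trials per setting. Mann-Whitney uses the normal approximation with tie and continuity corrections. The range covers 24, 27 and 30 per arm with normal, skewed and integer 0-10 data.

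| Procedure | 27 per arm | Range |
|---|---|---|
| ANOVA at 0.05, then t-tests at 0.05/3 | 4.2% | 3.9-4.2% |
| One prespecified Mann-Whitney pair | 4.8% | 4.5-4.9% |
| Two pairs sharing the liposomal arm, each at 0.05 | 8.7% | 8.5-9.0% |
| All three pairs, each at 0.05 | 11.9% | 11.6-12.2% |
| Kruskal-Wallis at 0.05, then pairs at 0.05 | 4.9% | 4.7-5.1% |

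**Disagreement on a single contrast.** This compares unadjusted Mann-Whitney with ANOVA/Bonferroni at 27 per arm, using normal data when arms differ. The two disagree in about 3% of trials when no arm differs, 5% when one arm differs by 1.01 SD, and 12% when it differs by 0.8 SD (assumed). For adjacent arms evenly graded over 1.01 SD (assumed), they disagree in 14-15%.

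**Power for one named pair.** Liposomal is placed 1.01 SD from two equal arms (assumed pattern).

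| Per arm | Mann-Whitney at 0.0167 | ANOVA/Bonferroni | Kruskal-Wallis gate |
|---|---|---|---|
| 24 | 81% | 85% | 89% |
| 27 | 86% | 89% | 93% |
| 30 | 91% | 93% | 96% |

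At 27 with graded arms, the largest contrast has 87%, 89% and 89%. The gate's advantage thus depends on the pattern of means and is not a reason for the finding.

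**The case against.** - **The specific section overrides the general one.** Section 6.2.2 is headed for the primary outcome and the Study Summary agrees with it, so Mann-Whitney is arguably intended. This is plausible, but the plan does not say so. On that reading the only stated multiplicity control disappears and the pair is still missing.
- **The sections could be combined.** An ANOVA at 0.05 followed by pairwise Mann-Whitney at 0.05 gives 3.7-5.1% error, so the level is essentially held. However, section 6.2 names Bonferroni t-tests as the follow-up, so this is not the written procedure.
- **No text prescribes three unadjusted tests with any success counting.** Correct. The 8.7% and 11.9% are conditional on that use.
- **The disagreement is mostly a matter of threshold.** Largely correct. The Mann-Whitney test is the significant one in over 95% of disagreements, chiefly because 0.05 is looser than a gated 0.0167. With both at 0.0167, disagreement falls to about 1% when no arm differs and 8-9% at 0.8 SD, but stays near 5% at 1.01 SD.
- **ANOVA/Bonferroni holds 5% only for one score per patient.** Correct. Testing several time points would inflate either route, by an amount the documents do not allow one to calculate.
- **d = 1.01 is borrowed.** Correct. Section 6.1 gives it for bupivacaine against placebo at 4-6 hours, not for liposomal bupivacaine or a 72-hour summary. The power and disagreement figures are illustrative; the error rates do not use d.

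**Conclusion.** The concern holds and must be fixed before any unblinded analysis. The plan contains two incompatible primary analyses, and one of them is incomplete for three arms. The claim is not that the error rate is 12%. It is that the text leaves it anywhere from about 4% to about 12%, according to later choices. The level is held if section 6.2 governs or one Mann-Whitney pair is prespecified. It is not held if two or three pairs are each tested at 0.05 and any success counts. These figures assume two-sided tests, one score per patient and 24 to 30 analysed per arm; they vary little across the data shapes tried.

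**What to change.** State one primary procedure in identical words in the Study Summary, 6.2 and 6.2.2, and delete the other. Any of these resolves the conflict:

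1. Kruskal-Wallis across the three arms at two-sided 0.05 and, only if significant, all three pairwise Mann-Whitney tests at 0.05. With three arms this is a closed test. In simulation, a truly null pair was falsely positive in about 5% of trials when the third arm differed by 1.01 SD.
2. Pairwise Mann-Whitney, each at 0.05/3 = 0.0167.
3. ANOVA followed by Bonferroni t-tests, as section 6.2 now reads.

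Define the one per-patient summary to which it applies, for example the time-weighted mean VAS from extubation to 72 hours or discharge, whichever is first. A raw sum would depend on the number of ratings: up to 72/2 = 36 at two-hourly intervals against 72/4 = 18 at four-hourly.

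Name liposomal against bupivacaine and liposomal against saline as the contrasts of main interest. Say whether bupivacaine against saline, the contrast behind the sample size, is primary or supportive.

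**Cost.** Choosing the test changes wording in three places. The summary also needs an edit to 3.4.1 and matching descriptions in 5.6, 7.4.2 and 9.1. No patients or procedures are added. Under option 1, no contrast can be claimed unless the overall test is significant.

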### **3.2 Allocation to Interventional Group**

The Neurosurgery Clinical Research Division (NCRD) will generate a randomization table by computer, which assigns subjects 1:1:1 to the three groups, in random blocks of 3 and 6. On the morning of the procedure, subjects will be assigned sequentially to the lowest unassigned randomization number. The surgeon performing the procedure and operating room staff will not be blinded to the intervention, since they will see whether the patient is receiving liposomal bupivacaine, bupivacaine or saline. However, all providers obtaining post-operative data from the patients will be blinded as to which treatment the patient received, in addition to the patient themselves.

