### **3.3 Study Measures**

A 10-cm VAS (where '0' is defined as 'no pain at all' and '10' as 'the worst possible pain' will be used to assess subjects' pain score. This will be assessed every 2 hours after extubation postoperatively while the patient is in the ICU, and every 4 hours after the patient has left the ICU, for 72 hours while inpatient, during waking hours, or until discharge in patients discharged prior to 72 hours post-op.

The Glasgow Coma score (GCS) (Teasdale & Jennett, 1974) will also be assessed at the above time points. Patients with GCS verbal score of <4 will be excluded from statistical analysis because of inability to respond to questions after extubation.

The cumulative doses of narcotics during this time period will also be measured. Intravenous narcotic medications will be given by the nurse taking care of the patient as rescue analgesic, as requested by the patient. If the patient requires more analgesics, the dosage will be increased as needed by the patient following standard clinical guidelines. Nursing personnel will be instructed to administer analgesic according to patient demand. The total rescue analgesic requirement will be noted at the above mentioned time intervals.

The duration of time between the end of the surgical procedure (extubation) and the first administration of rescue narcotic will be recorded.

The total length of ICU stay will be recorded. The total length of hospital stay will also be recorded.

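### Secondary endpoints: a paired t-test is named for three independent arms, it conflicts with the ANOVA in 6.2, and time to first narcotic has no rule for patients who never need one

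*Combined protocol and SAP*

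**What the plan says.** The design has three parallel arms. Section 3.1: "Patients will be randomized into one of three treatment groups: Bupivacaine, Liposomal Bupivacaine, and Saline". Section 3.2 describes a computer-generated table "which assigns subjects 1:1:1 to the three groups, in random blocks of 3 and 6". No crossover, matching or within-patient contrast is described.

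The analysis of secondary outcomes is stated three times:

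- Section 6.2: "The primary and secondary outcome variables will be examined for group-wise differences with Analysis of Variance statistics", and then "Significant differences in the means will then be subjected to Bonferroni's t-test".
- Section 6.2.2: "All other outcomes of interest (narcotic usage, ICU length of stay, total length of stay) will be analyzed using a paired t-test".
- Study Summary, Statistical Methodology: "A paired t-test will be used for all secondary endpoints".

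Section 3.4.2 lists five secondary endpoints: cumulative narcotic requirement, GCS, ICU stay, hospital stay, and time from end of surgery to first narcotic. Section 6.2.2 names only three of them. Time to first narcotic and GCS therefore come under the paired t-test through the Study Summary, and under ANOVA through 6.2.

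On rescue, Section 3.3 says "Intravenous narcotic medications will be given by the nurse taking care of the patient as rescue analgesic, as requested by the patient". On timing it says only "The duration of time between the end of the surgical procedure (extubation) and the first administration of rescue narcotic will be recorded". There is no censoring rule, assigned value or time-to-event method for a patient who receives no narcotic.

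**The concern.** A paired t-test needs a defined partner for each patient, and here there is none. It compares two groups where there are three, no contrasts are named, and it cannot use every patient when arm sizes differ. The word may be a slip for unpaired or pairwise, but it appears in two places. Even with that correction, a two-group test and a three-group test remain assigned to the same outcomes with no order of precedence.

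Time to first narcotic has a separate gap. Rescue is given on request, and Section 1.1 reports that bupivacaine scalp blocks reduce the need for it. Some patients may therefore have no event, possibly in different proportions by arm. A t-test or an ANOVA must either omit them or give them a value, so choosing between 6.2 and 6.2.2 does not settle the matter.

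Narcotic dose and time to first narcotic test the opioid-reduction aim in the study title. As written, the analyst would have to choose the pairing, the test and the handling of patients without an event, and nothing prevents those choices from being made once the data are visible.

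**Working it through.** **Inputs.** The plan gives no power or error figure for any secondary endpoint, so there is none to reproduce. From the documents: 90 patients in three arms, 90/3 = 30 per arm; 10% dropout (6.1), 30 × 0.9 = 27 per arm; significance level 0.05 (6.2), taken as two-sided; 72 h window (3.3). Never-rescued rates are not given and are assumed below.

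**1. Unequal arms.** If each arm keeps Binomial(30, 0.9) patients, two given arms end up equal with probability Σp(k)² = 0.174, and all three with Σp(k)³ = 0.035. When two arms differ, the mean difference is 2.20 patients, who have no partner and drop out of a paired test.

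**2. Dependence on row order.** With equal SDs and an observed difference of d SD, the paired statistic is t = d√n / √(2(1 − r)) on n − 1 = 26 df (critical value 2.056). Here r is the sample correlation created by whatever pairing is used. The unpaired statistic is d√(n/2) on 52 df and involves no r.

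- d = 0.60: unpaired t = 0.60 × √13.5 = 2.20, p = 0.032. The paired test loses significance when 2(1 − r) > (0.60 × 5.196/2.056)² = 2.30, that is, r < −0.15. Under random pairing r has SD of about 1/√26 = 0.196, so the probability is about Φ(−0.77) = 0.22. Simulation (100 data sets, 2,000 random pairings each) gave 22.2%.
- d = 0.30: unpaired p = 0.275. Significance would need r > 0.71; no sampled random pairing produced it.
- d = 0.80: (0.80 × 5.196/2.056)² = 4.09, which exceeds 4, the largest possible value of 2(1 − r). No pairing can change the conclusion.
- Share of pairings significant in between: 3.4% at d = 0.45, 43% at 0.55, 96.7% at 0.65.

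**3. Error and power of a single comparison** (100,000 simulated trials, 27 per arm). Type I error is 5.0% paired and 5.0% unpaired. Power at 0.75 SD is 75.6% paired and 77.1% unpaired.

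**4. Three comparisons, no true difference** (100,000 simulated trials). Chance of at least one false positive:

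- three paired tests at 0.05: 12.3%
- three unpaired tests at 0.05: about 12%
- ANOVA at 0.05, then unadjusted paired tests: about 5%
- ANOVA at 0.05, then unpaired tests at 0.05/3 = 0.0167 (the 6.2 route): 3.9%

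**5. Time to first narcotic** (two arms of 27, every test at 0.0167, 40,000 trials per row). Two models were used. In the first, times are exponential with rate −ln(c)/72, where c is the never-rescued share at 72 h. In the second, rescued patients have a median of 4 h in both arms and only the never-rescued share differs.

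| Never rescued, arm A vs B | Model | Log-rank | t-test, 72 h assigned | t-test, omitted | The two t-tests disagree |
|---|---|---|---|---|---|
| 0.5% vs 2% | exponential | 10% | 8% | 7% | 3% |
| 2% vs 10% | exponential | 30% | 27% | 14% | 17% |
| 5% vs 30% | exponential | 74% | 69% | 20% | 51% |
| 10% vs 40% | exponential | 70% | 64% | 11% | 54% |
| 2% vs 10% | 4 h median | 6% | 5% | 2% | 6% |
| 5% vs 30% | 4 h median | 41% | 52% | 1% | 52% |
| 10% vs 40% | 4 h median | 51% | 58% | 2% | 57% |

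Columns 3 to 5 are power. Omission is lowest in every row. Whether log-rank or assigning 72 h has more power depends on the model.

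**The case against.** Several points on the other side are fair.

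- Pairing alone does little damage: a single comparison keeps its 5% error and loses about 1.5 points of power, and row order matters only near p = 0.05. This stands. One can construct a worse case by sorting both arms on outcome before pairing, but nothing in the plan suggests doing so, and I give it no weight.
- The 12.3% comes from not adjusting, not from pairing; unpaired tests give about the same. Since 6.2.2 sits beneath 6.2, one could read the ANOVA as a gate for the later tests, which brings the figure to about 5%. This also stands, but the documents do not state that reading, and the gated test would still have no pairs.
- The rescue scenarios are assumed. In the exponential model the median time to rescue is 72 × ln 2 / (−ln c): about 13 and 22 h for 2% vs 10%, 17 and 41 h for 5% vs 30%, and 22 and 54 h for 10% vs 40%. These are long beside the four hours of pain reduction that Section 1.1 credits to bupivacaine blocks. The 4 h model was added for that reason, and it gives similar disagreement at the higher shares. The size of the effect in this trial is unknown; the absence of a rule is not in doubt.
- Section 3.3 sets its 72 h window for pain scores and narcotic doses, not expressly for time to rescue. Censoring there would set aside later first doses, and censoring at discharge may be informative. These are reasons to state the rule and report the counts, not to leave it unstated.

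**Conclusion.** The concern holds. The paired t-test is wrong for this design as written. It contradicts 6.2 for the same outcomes, and no text resolves the conflict. Time to first narcotic lacks a rule for patients without an event under either method.

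The harm is irreproducibility and open choice rather than bias. About one random pairing in five reverses a result at 0.60 SD, while none does at 0.80 SD. The false-positive chance ranges from 3.9% to 12.3% depending on which section is followed. For time to first narcotic, the two obvious ways of handling patients without an event disagree in anything from 3% to 57% of trials. That range depends entirely on assumed never-rescued shares, from 0.5% vs 2% to 10% vs 40%. All figures assume 27 evaluable patients per arm; those in steps 2 to 4 also assume normal outcomes.

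This should be fixed before analysis. It concerns secondary endpoints only; the primary outcome is outside this point.

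**What to change.** 1. **Study Summary and 6.2.2:** delete the paired t-test and refer to 6.2. For narcotic dose, ICU stay and hospital stay, use a three-group ANOVA followed by unpaired pairwise t-tests at 0.05/3 = 0.0167.
2. **Section 6.2:** exclude time to first narcotic from the ANOVA sentence.
3. **Section 6.2.2:** for time to first narcotic, specify Kaplan-Meier estimates by arm, a three-group log-rank test at 0.05, then pairwise log-rank tests at 0.0167. Time runs from extubation, as in 3.3. Patients without a narcotic are censored at 72 h or discharge, whichever comes first. Report by arm how many were discharged before 72 h; Section 4.1 gives typical stays of 1–2 weeks, so this should be uncommon.

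GCS then falls under 6.2 as written. It is recorded repeatedly, so the sponsor may also wish to name the per-patient summary to be analysed.

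The cost is wording in three places and no new data, since times, doses and stays are already recorded. The Bonferroni step lowers the power of one pairwise t-test at 0.75 SD from 77% to 61%, but 6.2 already requires it. Under the assumptions above, with one arm differing from the other two, the full log-rank procedure has power of 29%, 74% and 69% (exponential) or 6%, 41% and 51% (4 h model) at 2% vs 10%, 5% vs 30% and 10% vs 40%. Its chance of any false positive is about 4.5%.
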